6 MILESTONES

Study milestones are included in Table 1.

Table 1	Study Milestones
---------	------------------

Milestone	Data Included	Planned Date
Start of data collection	NA	2024
End of data collection	NA	2042
Registration in the HMA- EMA Catalogue	NA	Following Protocol Approval
Progress Report	NA	31 August 2024
Progress Report	Tentatively through 31 August 2024	31 August 2025
Progress Report	Tentatively through 31 August 2025	31 August 2026
Interim Analysis 1	Tentatively through 31 December 2026	31 December 2027
	(anticipated end of enrollment period)	
Progress Report	Tentatively through 31 December 2027	31 December 2028
Progress Report	Tentatively through 31 December 2028	31 December 2029
Interim Analysis 2	Tentatively through 31 December 2032	31 December 2033
	(all enrolled patients anticipated to reach 5 years of follow-up)	
Interim Analysis 3	Tentatively through 31 December 2037	31 December 2038
	(all enrolled patients anticipated to reach 10 years of follow-up)	
Final Report	Tentatively through 31 December 2042	31 December 2043
	(all enrolled patients anticipated to reach 15 years of follow-up)	

HMA-EMA Catalogue: Heads of Medicines Agencies and European Medicines Agency joint catalogue (former EU PAS Register); NA: not applicable

Milestones depicted in Figure 1 assume a 3-year enrollment duration with a study closure after the final enrolled patient has been followed for 15 years (i.e., Year 18). Study milestones and analysis dates (Table 1, Figure 1) are estimated and may shift due to final approval dates, enrollment needs and/or data availability.

Figure 1 Planned Data Collection Milestones

FU: follow-up; IA: interim analysis

Note: Timelines may shift slightly if enrollment is extended to 5 years duration.

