- **New malignancy**, including type and time to initial diagnosis, will be defined as any new malignancy, solid or hematologic, as reported to the transplant registry following the transplant date. Additional detail will be collected upon diagnosis, if available:

- TNM classification (for solid organ malignancies)
- Hematologic malignancy follow-up evaluation to be performed by the MAH as described in Section 12
- New or worsening (non-malignant) hematologic disorder, including time to diagnosis, may include the diagnosis of immune thrombocytopenia, autoimmune hemolytic anemia, autoimmune neutropenia, aplastic anaemia or other event, as reported to the transplant registry. Disorder status will be tracked at subsequent visits (e.g., stable, progressive, resolved), as applicable.
- **Mortality / Survival Status**, including time to event, will be based on the record in the respective registry:
 - Cause of death, as reported to the registries, will also be recorded
 - Date of last patient follow-up

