9.7.1 Definition of Study Periods

For safety and effectiveness outcome analyses within the Exa-cel and Allo-HSCT Cohorts the pre-transplant and post-transplant periods will be defined as described below and illustrated in Figure 2:

- **Day 0 (transplant date)** is defined as the day of exa-cel product or allogeneic donor cell infusion, depending on cohort, as reported to the registries.
- **The pre-transplant / baseline period** will be broadly defined as the period prior to Day 0, with the length of the period varying depending on the study measures being evaluated:
 - For the *primary disease severity* measures (see Section 9.3.4 Effectiveness Outcome Variables) and *disease-related therapies* (see Section 9.3.5), the baseline period will be defined as 1 year prior to initiation of the conditioning regimen.
 - For *laboratory measures*, baseline will be defined as the non-missing measure most proximal, but prior to treatment initiation. This includes effectiveness measures such as total Hb, Hb fractionation (e.g., % HbS for SCD) and serum ferritin (see Section 9.3.4) as well other laboratory measures (see Section 9.3.5).
 - For pre-transplant *disease-related end-organ damage or dysfunction* (see Section 9.3.5) baseline will be defined as any time prior to the transplant.
 - Other variables such as patient demographics, pre-transplant height, weight and health status will be as reported at the most recent time point prior to transplant.
- The post-transplant period will continue for up to 15 years after the final enrolled patient's Day 0. For each patient, Year 1 will include events, new diagnoses or findings, and/or therapies initiated (or continued) within the first 365 days after Day 0; Year 2 will include the same occurring from patient day 366 to day 730, etc. Year 1 will further include the following time intervals based on existing transplant registry reporting: Day 0 to Day 100, Day 100 to 6 months, and 6-month to 1-year reporting. All patients, both exa-cel treated or comparator, will be followed for up to 15 years. Patients will be censored to last reported timepoint only after 2 years of loss to follow-up.

Figure 2 Study Periods

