9.9.5 Loss to Follow-Up

Due to the targeted 15-year duration of follow-up, patients may be lost to follow-up over time. This may occur as adult and pediatric patients change their resident city, state, or country over time. Importantly, this loss to follow-up may be differential as patients experiencing the best post-transplant outcomes may reduce contact with their care providers. All efforts will be made to minimize losses to follow-up among the study participants, regardless of transplant type received or transplant outcome.

Measures to ensure long-term follow-up will include a combination of both transplant center and patient-specific interventions. In addition to standard patient-tracking routines, transplant centers participating in this sponsored study may receive additional education, patient tracking support, and/or tracking incentives based on annual patient follow-up. Patients, at the time of treatment

and/or initial consent / assent, will receive education on the importance of long-term follow-up contacts and, with additional consent / assent, may receive patient-friendly study updates.

The study progress reports and interim analysis reports will include statistics on the potential loss to follow-up for each study cohort. Analyses will be performed to understand if there are any systematic differences between patients lost to follow-up and remaining in the study to assess the direction and magnitude of potential bias.

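### The rule that censors patients at their last report only after 2 years of loss credits unobserved event-free time at interim data cuts, with a modest effect that is largest at Interim Analysis 1

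*Protocol*

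**What the plan says.** Protocol Section 9.7.1, which defines the periods for the safety and effectiveness analyses in both treatment groups, fixes the censoring rule: "Patients will be censored to last reported timepoint only after 2 years of loss to follow-up". It gives no end date for a patient whose silence is shorter than 2 years when the data are cut.

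Other passages bear on it:

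- Section 9.3.3 collects, under mortality and survival status, the "Date of last patient follow-up". Censoring at last contact is therefore feasible for everyone.
- Sections 9.7 and 9.7.3 plan overall survival, cumulative incidence and per-timepoint proportions for malignancy, hematologic disorder and death. These outcomes serve the primary objective.
- Section 9.9.4 rules out imputing missing data.
- Section 9.9.5 warns that "this loss to follow-up may be differential as patients experiencing the best post-transplant outcomes may reduce contact with their care providers".
- Section 6 sets the timing. "Milestones depicted in Figure 1 assume a 3-year enrollment duration". Interim Analysis 1 uses data "Tentatively through 31 December 2026", the expected end of enrollment. Interim Analysis 2 uses data "Tentatively through 31 December 2032", Interim Analysis 3 "Tentatively through 31 December 2037" and the final report "Tentatively through 31 December 2042".

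**The concern.** The sentence names the right censoring date and then, through the word *only*, withholds it until 2 years have passed. Until then the patient has no stated end of observation. In a survival or cumulative incidence curve, the natural consequence is that the patient remains at risk and event-free to the cut. Any malignancy or death after the last report is unknown, yet the time still counts in the denominator. Once 2 years have passed the patient is moved back to the last report, so the same person's follow-up can shrink between one analysis and the next.

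Interim Analysis 1 is the most exposed. No patient can have more than 3 years of follow-up, so nearly all losses are recent. Section 13 sends interim results into the periodic safety reports, and the error makes risks look smaller than last-contact censoring would show.

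**Working it through.** The protocol states no figure for this rule, so there is nothing of its own to reproduce.

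**Inputs from the protocol.** Three-year enrollment. Data cuts 3, 9, 14 and 19 years after the start of 2024, giving follow-up per patient of 0–3, 6–9 and 11–14 years at the interim analyses and a 15-year cap at the end.

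**Assumptions.** Uniform accrual; event rate h = 3% per year; loss rate λ of 5%, 10% or 20% per year; same event risk before and after loss; events after loss unknown. Retained patients are taken as observed up to the cut.

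**Step 1: how many lost patients are still uncensored at Interim Analysis 1** (λ = 5%).
- Share lost: 1 − (1 − e^(−0.15))/0.15 = 0.071.
- Share lost at least 2 years before the cut: (1/3)[1 − (1 − e^(−0.05))/0.05] = 0.008.
- Uncensored among the lost: 1 − 0.008/0.071 ≈ 88%. With 200 exa-cel patients, about 14 are lost and about 13 of them are carried to the cut.
- By simulation, the uncensored share falls to 23% at Interim Analysis 2, 12% at Interim Analysis 3 and under 1% at the end.

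**Step 2: the estimated hazard.** At time t since transplant (t ≤ 2), let
- A(t) = share truly under observation = [(3 − t)/3]·e^(−(λ+h)t)
- B(t) = share lost but carried = (1/3)∫₀ᵗ λe^(−(λ+h)l)·[min(3, l + 2) − t] dl

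The rule estimates h·A/(A + B) instead of h. For λ = 5%:
- t = 1: A = 0.6154, B = 0.0239, ratio 0.963
- t = 2: A = 0.2840, B = 0.0227, ratio 0.926

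**Step 3: 2-year incidence.** Averaging the ratio over 0–2 years by Simpson's rule: (1 + 4 × 0.963 + 0.926)/6 = 0.963. The estimate is 1 − e^(−0.06 × 0.963) = 5.61%, against a true 1 − e^(−0.06) = 5.82%.

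| Loss per year | Interim 1, 2-year (true 5.82%) | Interim 2, 8-year (true 21.34%) |
|---|---|---|
| 5% | 5.61% (3.6% low) | 21.04% (1.4% low) |
| 10% | 5.41% (7.1% low) | 20.75% (2.7% low) |
| 20% | 5.03% (13.6% low) | 20.20% (5.3% low) |

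The relative error is nearly the same at 1% events per year (3.7%, 7.2% and 13.7% at Interim Analysis 1). At Interim Analysis 2 it sits in the tail of the curve: the 5-year estimate is only 0.1–0.2% low. At the final analysis the rule and last-contact censoring agree (15-year incidence 36.30% against 36.31% at 5% loss).

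**Step 4: if retained patients between reports are also carried to the cut.** A simulation on the protocol's reporting schedule gives a 2-year estimate at Interim Analysis 1 of 4.7% with no loss, then 4.5%, 4.3% and 3.9% at 5%, 10% and 20% loss. That is 19–32% low. About 19% of it is present with zero loss, so most of it is reporting lag rather than loss. Censoring at the last report returns about 5.8%.

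**Step 5: if lost patients differ in risk.** Estimated rate divided by true rate, 10% loss per year:

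| Risk after loss | Interim 1: rule / last contact | Interim 2 (8-year): rule / last contact |
|---|---|---|
| Half | 0.98 / 1.05 | 1.15 / 1.17 |
| Same | 0.93 / 1.00 | 0.98 / 1.00 |
| Double | 0.85 / 0.92 | 0.77 / 0.79 |

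The rule is always below last-contact censoring. Against the truth it is low at Interim Analysis 1 in every case, but not later if healthier patients leave.

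**The case against.** **The sentence may only define when a patient is declared lost.** Nothing in the protocol says outright that silent patients are carried forward. The last follow-up date is collected, and crediting unseen time sits badly with the ban on imputation. If everyone in fact ends at the last report, there is no bias. This reading is possible, but *only* points the other way, and an analysis plan that follows the protocol would inherit the rule as written.

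**A reader might infer a 20–30% understatement.** The protocol does not support that as the size of this defect. The sentence concerns loss to follow-up, and most of that figure arises in retained patients whose next annual form is not yet due. It applies only if such patients count as silent under the rule. Table 1 also leaves 12 months between each cut and its report, in which later forms could settle status at the cut; the protocol does not say whether they will be used.

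**A reader might infer bias between exa-cel and allo-HSCT from Section 9.9.5.** That section describes loss that depends on outcome, not on cohort, and promises equal retention effort for both transplant types. Unequal credit between cohorts is possible but not established. One real asymmetry exists: serious adverse events reach the marketing authorization holder directly for exa-cel recipients only, so if those reports fed the curves, only one cohort would be corrected.

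**The practical effect is small.** The study is descriptive, without prior hypotheses, and Interim Analysis 1 is reported by registry and disease. With a third of 200 exa-cel patients in Europe, split evenly by disease (an assumption), a cohort has about 33 patients and 33 × 1.5 years × 3% ≈ 1.5 expected events. A 4–7% shift is about 0.1 event. This stands, and it limits the severity.

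**Conclusion.** The rule is wrong as written, with minor to moderate consequence. Read literally, it credits unobserved event-free time to patients lost for less than 2 years, and so lowers incidence and mortality estimates relative to last-contact censoring. Under the stated assumptions (3% events per year, uniform accrual, non-informative loss of 5–20% per year) the shortfall is about 3–14% relative at Interim Analysis 1, about 1–5% at 8 years in Interim Analysis 2, and close to nil at the end. The loss and event rates are assumptions, because the protocol gives none.

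It would go too far to say that safety risks are understated at every analysis. If the healthiest patients leave, both methods overstate risk at the later interim analyses, and last-contact censoring does not cure that.

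**What to change.** Replace the sentence in Section 9.7.1 with: *At every data cut, event-free patients are censored at the date of last patient follow-up; 2 years without contact is used only to classify a patient as lost to follow-up in retention summaries.*

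This settles the matter under either reading, and also covers retained patients between reports. The date is already collected, so no new data are needed. The cost is one sentence and slightly shorter stated follow-up at the interim analyses. The comparison of lost with retained patients planned in Section 9.9.5 is still needed, because the change does not address outcome-dependent loss.

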9.7.2 Demographics and Baseline Characteristics

The following demographic and baseline characteristics will be summarized for each cohort for the pre-transplant period:

- Primary disease diagnosis variables (Section 9.3.1)
- Baseline demographic measures (Section 9.3.5)
- Baseline health status measures (Section 9.3.5)
- Baseline disease severity measures (Section 9.3.4)
- Baseline Hb measures (Section 9.3.4)
- Baseline iron concentration measures (Section 9.3.4)
- Baseline disease-related end-organ damage or dysfunction diagnoses (Section 9.3.4)
- Baseline iron overload management (Section 9.3.4)
- Baseline disease-related therapies (Section 9.3.5)
- Baseline additional laboratory measures (Section 9.3.5)
- Additional transplant-related details (Section 9.3.5)

Any demographic or health differences between US and European patients will be summarized in the interim and final study reports.

The baseline demographic and clinical characteristics of the exa-cel and comparator patients will be compared descriptively. Any major differences identified between the cohorts will be accounted for using stratification or modelling, as needed and feasible based on patient counts.

9.7.3 Safety Analyses

Safety outcomes will be evaluated for each cohort from each registry at each time point of the post-transplant period. In addition to the separate analyses within each registry, pooled analyses of the safety outcomes listed below will be performed at pre-specified timepoints (after a 5-, 10-, and 15-year duration of follow-up is accrued for all enrolled patients), unless substantial heterogeneity is observed between the two registries. Any potential issues precluding variable harmonization across the two registries will be discussed in the analysis reports. Analyses will be performed overall and in subgroups by patient age group, genotype, country, and/or other category, as appropriate and if sufficient data are available. Additional analyses may be performed for outcomes deserving further investigation if sufficient data are available. Statistical testing may be performed comparing the frequencies or rates of outcomes from the TDT Exa-cel and TDT Allo-HSCT Cohorts, and the SCD Exa-cel and SCD Allo-HSCT Cohorts, if sufficient data are available.

• Neutrophil Recovery

Proportion of patients reaching the neutrophil recovery threshold, with the corresponding 95% CI, will be calculated at each timepoint of the post-transplant period until all patients have reached neutrophil recovery.

Time to neutrophil recovery, in days, will be calculated for each patient from Day 0, as reported by the registries.

The proportion of patients who recovered neutrophils by specific timepoints of interest (for example, by Day 42) will also be calculated.

Cumulative incidence curves detailing time to neutrophil recovery may be produced.

• Platelet Recovery

Platelet recovery threshold will vary for SCD and TDT cohorts.

Proportion (with 95% CI) of patients reaching the platelet recovery threshold will be calculated at each timepoint of the post-transplant period until all patients have reached platelet recovery.

Time to platelet recovery, in days, will be calculated for each patient from Day 0, as reported by the registries.

Cumulative incidence curves detailing time to platelet recovery may be produced.

• New Malignancy

Proportion (with 95% CI) of patients diagnosed with a new hematologic malignancy will be calculated for each timepoint of the post-treatment period.

Proportion (with 95% CI) of patients diagnosed with a new solid malignancy will be calculated for each follow-up of the post-treatment period.

Cumulative incidence of new malignancy over the entire post-HSCT period will also be reported.

Specific malignancy types will be reported as the proportion(s) of all malignancies reported.

TNM classification, where available, will be reported for the subset of solid tumors.

• New or Worsening Hematologic Disorder

Proportion (with 95% CI) of patients diagnosed with a new (or worsening) hematologic disorder will be calculated for each timepoint of the post-treatment period.

Cumulative incidence of new hematologic disorders over the entire post-HSCT period will also be reported.

• Mortality / Survival Status

Proportion (with 95% CI) of deaths (overall and by cause) will be calculated for each timepoint of the post-treatment period.

Overall survival over the entire post-HSCT period will also be reported.

Individual line listings will be provided for the key safety outcomes of hematologic malignancy diagnosis and mortality.

9.7.4 Effectiveness Analyses

Effectiveness analysis outcomes will be evaluated for each cohort from each registry for each post-transplant follow-up period. Analyses will be performed overall and in subgroups by patient age group, genotype, and/or other category, as appropriate and if sufficient data are available. Additional analyses may be performed for outcomes deserving further investigation if sufficient data are available. Statistical testing may be performed comparing the frequencies or rates of outcomes from the TDT Exa-cel and TDT Allo-HSCT Cohorts, and the SCD Exa-cel and SCD Allo-HSCT Cohorts, if sufficient data are available.

- For the primary disease severity measures, descriptive statistics for the number of events in the 1 year prior to the preparative regimen initiation and at each of the post-transplant follow-up periods will be reported:
 - Number of RBC transfusion events (TDT and SCD)
 - Number of severe VOC events (SCD only)

Proportions of patients who are RBC transfusion-free, severe VOC-free or severe VOC hospitalization-free (as appropriate) will also be reported at each timepoint of the post-transplant periods.

Time RBC transfusion-free or VOC-free, from Day 0 to the most recent event, will also be summarized.

- **Hb measures** (total Hb, % HbF, % HbS [where relevant]) will be summarized as continuous variables for each timepoint of the post-transplant period, with a 95% CI, among patients with an observation.
- **Iron concentration measures** (serum ferritin, LIC, CIC) will be summarized as continuous variables for each timepoint of the post-transplant period, with a 95% CI, among patients with an observation.

Absolute change from baseline may be calculated for patients with non-missing baseline and post-transplant years.

• New disease-related end-organ damage or dysfunction diagnoses will be summarized for each timepoint of the post-transplant period as the proportion of patients with a new diagnosis (i.e., categorical variables), with a 95% CI.

Cumulative diagnoses over the entire post-HSCT observation period may be reported for select diagnoses.

• Use of iron overload management tools (chelation therapy, phlebotomy) will be summarized for each timepoint of the post-transplant follow-up period as the proportion of patients receiving therapy (i.e., categorical variables).

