9.3.4 Effectiveness Outcome Variables

Variables described in this section are to: (i) characterize disease status at baseline and (ii) allow direct and indirect assessment of the effectiveness and durability of the transplant. Characterization of the type and number of transfusions (among TDT and SCD patients) and/or severe VOC events (SCD patients only) pre- and post-transplant allows determination of whether overt disease symptomatology has been corrected with the transplant. Hb measures, including total Hb concentration as well as Hb fractionation (e.g., % HbS among patients with SCD), allows tracking of graft uptake and function at a more cellular level than the symptomatic measures. Iron concentration and iron overload management are secondary measures of graft function, as cessation of primary symptomology (transfusion dependence) should lead to measurable decreases in iron burden and a reduced need for iron overload therapies over time. Measures of organ dysfunction at baseline and over time are also secondary measures of graft function as successful correction of the underlying genetic deficiency is expected to prevent further accumulation of organ damage over time and/or prevent new disease-related organ damage events from occurring. These measures encompass the core effectiveness assessment for the transplant.

The following effectiveness outcomes will be recorded:

- **Primary disease severity measures** will be recorded pre- and post-transplant as summarized in the schedule of data collection presented in Section 9.3.6. Specifically, pre-transplant these events will be quantified for the 1 year (12 months) preceding initiation of the conditioning regimen:
 - RBC transfusion events (TDT and SCD) to be defined as the receipt of RBCs for the purpose of primary disease management (i.e., anemia). Number of RBC transfusions and number of units transfused will be recorded pre- and post-transplant (as available) as summarized in the schedule of data collection. Time from HSCT to most recent transfusion will be recorded.
 - Severe VOC events (SCD only): Number of severe VOC events will be recorded pre- and post-transplant as summarized in the schedule of data collection presented in Section 9.3.6. Time from HSCT to most recent severe VOC event will be recorded.

Severe VOC events will include any/all of the following events:

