- Acute pain events, to be defined as an acute pain event that requires hospitalization or a visit to a medical facility for treatment
- Acute chest syndrome events, to be defined as clinical evidence of the presence of a new pulmonary infiltrate associated with pneumonia-like symptoms, pain, cough or fever, and requiring hospitalization or a visit to a medical facility for treatment
- Priapism events, to be defined as a priapism event lasting >2 hours and requiring hospitalization or a visit to a medical facility for treatment
- Splenic sequestration event, to be defined by an enlarged spleen, left upper quadrant pain, and an acute decrease in Hb concentration of $\geq 2 \text{ g/dL}$ and requiring hospitalization or a visit to a medical facility for treatment
- Hospitalization for any severe VOC event during the reporting period, to be recorded in the post-HSCT period only
- **Hb measures** will be recorded pre- and post-transplant as summarized in the schedule of data collection presented in Section 9.3.6:
 - Hb concentration, grams per deciliter (g/dL)
 - Hb fractionation measured to assess the relative proportion of Hb variants produced, including (at minimum): percent HbF, HbS (for SCD, only)
- **Iron concentration measures** will be recorded pre- and post-transplant as summarized in the schedule of data collection presented in Section 9.3.6:
 - o Serum ferritin concentration, micrograms per liter ($\mu g/L$)
 - Liver iron concentration (LIC), measured by magnetic resonance imaging (MRI), milligrams per gram dry weight (mg/g)
 - Cardiac iron concentration (CIC), measured by obtaining MRI T2* (msec)
- **Disease-related end-organ damage or dysfunction** diagnoses, including approximate time to initial diagnosis if available, will be recorded pre- and post-transplant as summarized in the schedule of data collection presented in Section 9.3.6:
 - o Anemia
 - o Arrythmia
 - Central nervous system event (stroke, ischemic or hemorrhagic; transient ischemic attack)
 - Diabetes
 - Growth retardation / impairment
 - Heart failure, congestive
 - Hepatomegaly
 - Hypogonadism

- o Hypothyroidism
- Liver cirrhosis
- Liver fibrosis
- Myocardial infarction
- Osteopenia or osteoporosis
- Osteonecrosis
- Pulmonary hypertension
- Retinopathy, SCD-related
- Renal failure
- Splenectomy, surgical
- Splenomegaly (among those with spleens)
- Ulcer(s) of the leg
- Venous thromboembolism (deep vein thrombosis, pulmonary embolism)

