9.3.5 Additional Key Variables

Additional key variables encompass general patient characteristics (e.g., demographics and health status), supporting transplant and laboratory measures (e.g., complete blood count [CBC]), and additional transplant-related complications (e.g., infection, bleeding, veno-occlusive liver disease) that may be of importance. The hematopoietic cell transplantation comorbidity index (HCT-CI) captures a wide range of co-existing diseases or organ impairments relevant to HSCT outcomes such as renal or hepatic impairment and prior history of malignancy. These variables may be considered as covariates for subgroup analyses and/or allow to further characterize the post-transplant outcomes.

Additional key variables will be recorded pre- and/or post-transplant as summarized in the schedule of data collection presented in Section 9.3.6 to assess patient demographics and general health status.

• Demographics

- Age at initial disease diagnosis
- Age at transplant
- o Sex
- Race, Ethnicity (US only)
- Country of transplant

- Payor type (US only)
- Health status
 - Performance score (Karnofsky for ages ≥ 16 years or Lansky for ages < 16 years)
 - Hematopoietic cell transplantation comorbidity index (HCT-CI) items¹³
 - Height
 - o Weight
 - Smoking history
- Additional transplant details will be recorded at the time of transplant, as available.
 - Preparative regimen (myeloablative, reduced-intensity, non-myeloablative, unknown)
 - Conditioning agent(s), including dose, start date, as available
 - \circ CD34⁺ cell infused dose, if available
 - Mobilization agent (Exa-cel Cohorts only)
 - Product identification (Exa-cel Cohorts only)
 - Donor type (Allo-HSCT Cohorts only)
 - Donor matching (Allo-HSCT Cohorts only)
 - Cell source (Allo-HSCT Cohorts only)
- **Disease-related therapy** use will be recorded pre- and post-transplant as summarized in the schedule of data collection presented in Section 9.3.6, to be defined as prescription or in-hospital use (i.e., for opioids) of the below agents or interventions at any time in the 1 year prior to HSCT (pre-transplant) or since the prior visit (post-transplant):
 - o Crizanlizumab
 - o Hydroxyurea / Hydroxycarbamide
 - o L-glutamine
 - Luspatercept
 - Narcotics / Opioids (for indication-related pain, only)
 - Non-narcotic and/or nonsteroidal anti-inflammatory drug analgesics (for indication-related pain, only; if available)
 - Voxelotor

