9.7.5 Other Analyses

Additional key outcomes will also be evaluated for each cohort from each registry for each time point of the post-transplant period. Findings will be summarized as categorical or continuous measures, as appropriate:

• Post-transplant complications

- Post-transplant health status measures
- Post-transplant disease-related therapies
- Post-transplant additional laboratory measures, including relevant CBC results at each available timepoint throughout the study duration
- Post-transplant pregnancies

In addition to all analyses of the pre-specified outcome variables (Section 9.3.3 through 9.3.5) for both the exa-cel and allogeneic HSCT cohorts, Serious Adverse Events (SAEs) among participating exa-cel recipients reported to the sponsor per Section 11 will be provided with each study report as a summary tabulation (proportion of exa-cel treated patients with SAE reports, by type) and in a listing format. Findings from the hematologic malignancy evaluation (Section 12) will also be provided, where available.

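### The RBC transfusion definition, read literally, omits preventive and exchange transfusion in SCD, and event-free proportions are not linked to disease-modifying therapy in the same interval

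*Protocol*

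**What the plan says.** Three parts of the protocol bear on this point.

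- **Transfusion events (9.3.4).** The definition reads "RBC transfusion events (TDT and SCD) to be defined as the receipt of RBCs for the purpose of primary disease management (i.e., anemia". It applies to the year before conditioning and to every post-transplant interval, and it determines what centres report.
- **Event-free status (9.3.4 and 9.7.4).** Severe VOC is defined by clinical events alone; for example, "Acute pain events, to be defined as an acute pain event that requires hospitalization or a visit to a medical facility for treatment". Section 9.7.4 then says "Proportions of patients who are RBC transfusion-free, severe VOC-free or severe VOC hospitalization-free (as appropriate) will also be reported at each timepoint", with no condition on concurrent treatment. Section 9.3.4 explains the purpose: recording transfusions and severe VOCs before and after transplant "allows determination of whether overt disease symptomatology has been corrected with the transplant".
- **Concurrent therapy (9.3.5 and 9.7.5).** Hydroxyurea, crizanlizumab, L-glutamine, luspatercept, voxelotor, analgesics and a write-in category are recorded for use "at any time in the 1 year prior to HSCT (pre-transplant) or since the prior visit (post-transplant". Section 9.7.5 lists "Post-transplant disease-related therapies" as a separate summary for each cohort and timepoint. Section 9.3.5 permits such variables as covariates but does not require it.

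**The concern.** Two problems follow, and the first is the more serious.

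The transfusion definition is tied to anaemia. Section 9.2 of the same protocol says that SCD care also aims at preventing stroke and other vaso-occlusive events. A patient who receives simple or exchange transfusion for that purpose has, on a literal reading, no transfusion event. Such a patient can be scored transfusion-free at baseline and at follow-up, and VOC-free because the transfusions are working. Because the definition decides what is entered on the form, no later analysis can recover the uncounted transfusions.

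Second, a patient who resumes hydroxyurea and has no VOC is VOC-free in the table. For that patient, the reading in 9.3.4 that the transplant corrected the symptoms does not follow. Long-term effectiveness, alone and against allo-HSCT, is the secondary objective, so what these proportions mean over 15 years matters.

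**Working it through.** The protocol states no event-free rate, therapy-use rate, power or margin for these outcomes, so there is no figure to reproduce. The only related figure is study size: at least 100 TDT + 100 SCD = 200 exa-cel patients (9.5), with about as many comparators.

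**Step 1: the definition.** Section 9.3.4 glosses the purpose of transfusion with *i.e.*, not *e.g.*, which restricts it to anaemia. Section 9.2 names prevention of stroke and vaso-occlusion as an aim of SCD care. No section says whether RBCs given for that aim count. If *t* of 100 SCD patients receive only preventive transfusion in an interval, the literal rule puts all *t* among the transfusion-free. The proportion is then *t* points higher than if those transfusions counted: 5 to 15 points for an assumed *t* of 5 to 15, and none if *t* = 0. The same rule applies to the baseline year, so the within-patient comparison is affected too, and the direction there is not known.

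**Step 2: two separate tables do not give the joint proportion.** Assume 90% are VOC-free and 15% are on disease-modifying therapy. The share both VOC-free and off therapy lies between 90 − 15 = 75% (all treated patients are VOC-free) and min(90, 100 − 15) = 85% (as many treated patients as possible have had a VOC). The margins leave a 10-point range.

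**Step 3: size of the shift within a cohort (assumed inputs).** Let *V* be the event-free proportion as planned and *u* the share of event-free patients on a disease-modifying drug or preventive transfusion. The proportion event-free and off therapy is *V*(1 − *u*).

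| *V* | *u* = 0 | 5% | 10% | 20% |
|---|---|---|---|---|
| 0.90 | 0.900 | 0.855 | 0.810 | 0.720 |
| 0.80 | 0.800 | 0.760 | 0.720 | 0.640 |

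With *V* = 0.90 and n = 100, the 95% half-width is 1.96 × √(0.90 × 0.10 / 100) = 0.059. The shift *Vu* exceeds it once *u* > 0.059 / 0.90, about 7%. Effectiveness is analysed by registry, and 9.5 expects about one third of patients from Europe. If that split holds for SCD, the cohorts are about 33 and 67. The half-widths are then 0.102 and 0.072, and the thresholds about 11% and 8%.

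**Step 4: between cohorts (assumed inputs).** Suppose 0.75 are truly event-free off therapy in both cohorts. The planned proportion is then 0.75 / (1 − *u*).

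- *u* = 20% versus 5%: 0.938 versus 0.789, a difference of 0.148 that does not reflect the graft. A two-sided 5% test with 100 per arm would flag it about 87% of the time.
- *u* = 10% versus 5%: 0.833 versus 0.789, a difference of 0.044, flagged about 12% of the time.
- Equal *u*: no difference.

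The 100-per-arm figures would require pooling of the registries, which for effectiveness is only optional.

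**The case against.** The strongest reply is that the protocol does not ignore these therapies. They are recorded at every visit in all cohorts and summarised at each timepoint. Section 9.9.3 says the outcomes will be considered together with data on symptoms and therapies when durability is characterised. Transfusions are an outcome in SCD as well as TDT, and HbF and HbS fractions track the graft directly. The study is descriptive, has no prior hypotheses, and makes between-cohort testing optional. Cross-tabulating event-free status with therapy is ordinary analysis-plan detail, and that plan is not shown. All of this stands. It limits the second problem to a missing link between variables that are already collected.

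It does not answer the first problem. One could say that the purpose restriction is there to keep peri-transplant support out of the count, and that preventive transfusion is not expressly excluded. The first part is a sensible aim, but tying the purpose to anaemia goes further than that aim needs, and centres will follow the definition they are given.

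A reader might also infer that the iron measures share the fault, since 9.3.4 argues that "cessation of primary symptomology (transfusion dependence) should lead to measurable decreases in iron burden" while chelation and phlebotomy lower iron whatever the graft does. The documents do not support this. The same sentence of 9.3.4 also expects less need for iron-lowering treatment, and chelation and phlebotomy are effectiveness outcomes reported in 9.7.4 alongside the iron measures. Splitting iron change by post-transplant chelation would condition on something that iron level and graft function themselves drive.

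**Conclusion.** The point holds in two parts. The transfusion definition, read literally, leaves out preventive and exchange transfusion in SCD. It should be corrected in the protocol because it governs data capture. The event-free proportions are not linked to disease-modifying therapy in the same interval; an added proportion would close that gap cheaply, and the analysis plan may already provide it.

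A reader might go further and say that the protocol counts drug-maintained patients as transplant successes, or that the comparison with allo-HSCT is biased. Neither is supported. No success or responder endpoint is defined, and bias between cohorts needs different therapy use, on which the documents give no figure. Nor is there a case for replacing the planned proportions: being free of an event is a legitimate quantity to report.

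The size of the effect is unknown. The figures above rest on assumed event-free and therapy-use rates, and the effect is zero if no patient is on such therapy. The primary safety objective is untouched.

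**What to change.** 1. **Section 9.3.4.** Remove the anaemia-only restriction. Count every RBC transfusion given for the haemoglobinopathy, simple or exchange, including for stroke or VOC prevention. Record peri-transplant support separately through a reason field on the study-specific forms. Section 9.3 says these forms will be finalised upon protocol approval, so the change is cheapest before then.
2. **Section 9.7.4.** Keep the current proportions. Beside them, and identically in all cohorts, report (a) the proportion event-free with no disease-modifying therapy in the same reporting interval, using the 9.3.5 list without analgesics, and (b) VOC-free status cross-classified by transfusion.

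The cost is one form field, one table, and post-transplant proportions that may look slightly less favourable. Two limits should be stated with the results. Therapy is recorded as any use since the prior visit, so brief use counts as on therapy. Individual VOC dates are not captured (9.9.1), so VOC and therapy cannot be ordered within an interval.
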